($P < 0.001$) associated with the presence of ocular surface disease, hyperemia, ocular signs, symptoms upon and between instillation, and the use of tear substitutes. Apparently, patients in the present study are satisfied with their treatment; 89% expressed satisfaction compared with only 11% who professed dissatisfaction. The results suggest that even if local adverse events and ocular surface disease, in particular, contribute to glaucoma patient dissatisfaction, only a minority of patients expressed such dissatisfaction. At the time of the study, most (94%) of the patients included were receiving preserved preparations. Further studies should evaluate the influence of preservative on patient satisfaction.

Recent reports indicate that more than 90% of patients with glaucoma fail to refill their ocular medications continuously during the first year of therapy and that less than 60% continue to refill eye drop prescriptions at 1 year (Friedman et al, 2007, *Inv Ophth Vis Sci*; Nordstrom et al, 2005, *Am J Ophth*). It has been suggested that medication adherence may be improved substantially by choosing a drug that needs to be taken less often (Norell, 1981, *Am J Ophthalmol*).

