2.3 Exclusion criteria

A patient will be excluded from the study if any of the following exclusion criteria apply:

- Current enrolment in other clinical trial.
- Patient with uncontrolled IOP ≥ 21 mmHg.
- Pregnant or nursing (lactating) women, where pregnancy is defined as the state of a female after conception and until the termination of gestation, confirmed by a positive hCG laboratory test
- Patients in treatment for ocular diseases (including OH or OAG) with more than one therapy.

- Patient with hypersensitivity to the active substance or to any of the excipients of this medicinal product.

3. Study endpoints

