3.1 Primary endpoints

The primary endpoints of the study is the Proportion of patients reporting high adherence to TRAVATAN® at 24 weeks defined as a Morisky Medication Adherence Scale (MMAS-4) score equal to 0.

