5.3 Final visit (week 24)

During the final visit, the following will take place: administration of the MMAS-4 questionnaire, calculation of the Medication Persistence Ratio and the following data will be recorded: description of potential factors associated with non-adherence, treatment discontinuations and adverse events.

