5.5 MPR

The Medication Persistence Ratio (MPR) was defined as the number of days without receiving medication after study enrolment divided by the number of days participating in the study. High adherence was defined as a value less than 0.20.

6. Treatment and concomitant medication

Since this is an observational, non-interventional study, the treatment schedule is defined according to investigator’s criteria. Treatment with TRAVATAN® should be according to the indication for treatment as defined in the Summary of Product characteristics (SmPC) and according to standard clinical practice. During this non interventional study, any changes and/or additions to the concomitant medications are allowed according to investigator’s criteria. All concomitant medications will be recorded on the CRF.

7. Treatment discontinuation

A patient should be withdrawn from the study if:

- according to the investigator’s criteria treatment with TRAVATAN® should be discontinued
- the patient withdraws her consent for participation in the study
- any of the exclusion criteria becomes applicable.

The reason of patient’s withdrawal should be recorded on the CRF.

8. Safety assessments

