All pregnancies that occur during the study, or within 14 days of completion of the study, are to be reported immediately to the individual identified in the clinical study personnel contact information section of this protocol, and the physician must provide the LSO with the pregnancy form. The process for reporting a pregnancy is the same as that for reporting an SAE. All patients who become pregnant will be monitored to the completion or termination of the pregnancy. If the pregnancy continues to term, the outcome (health of the infant up to 8 weeks of age), including spontaneous or voluntary termination, details of birth, and presence or absence of any birth defect, congenital abnormalities, or maternal and newborn complications, will be reported to the sponsor. Any complication of pregnancy will be reported as an AE or SAE, as appropriate. For pregnancies of partners of men participating in the study, the Sponsor's Pharmacovigilance (PhV) Department will determine the procedure to appropriately follow up after notification as described above. All partners who become pregnant and provide appropriate consent to Sponsor's PhV will be monitored to the completion or termination of the pregnancy.

If the pregnancy does not continue to term, 1 of the following actions will be taken:

- For a spontaneous abortion, report an SAE.
- For an elective abortion due to developmental anomalies, report as an SAE.

- For an elective abortion **not** due to developmental anomalies, report on the pregnancy form.

9. Sample size

In order to calculate a 95% confidence interval for the proportion of patients reporting high adherence to TRAVATAN® at 24 weeks, which is expected to be 80% with a margin error (Δ) (Okeke et al, 2009) no more than 2%, the required sample size is at least 1537 patients. A total sample size of at least 1843 patients (20% additional) will allow compensation for incomplete datasets.

10. Statistical methods

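### Section 7 takes patients out of the study when TRAVATAN is stopped or an exclusion criterion arises, so they have no week-24 MMAS-4; if they are left out, adherence among all enrolled is likely to be overstated

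*Protocol*

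**What the plan says.** Section 7 opens its list of withdrawal reasons with "A patient should be withdrawn from the study if". The first reason is that "according to the investigator’s criteria treatment with TRAVATAN® should be discontinued", the second is withdrawn consent, and the third is that "any of the exclusion criteria becomes applicable". The exclusion criteria in Section 2.3 include "Patient with uncontrolled IOP ≥ 21 mmHg" and treatment of ocular disease with more than one therapy. The reason for withdrawal goes on the CRF.

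The primary endpoint in Section 3.1 is the "Proportion of patients reporting high adherence to TRAVATAN® at 24 weeks", meaning an MMAS-4 score of 0. Section 5.3 places the measurement: "During the final visit, the following will take place: administration of the MMAS-4 questionnaire". The scale is also given at week 8. No data collection after withdrawal is described.

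Section 9 states "A total sample size of at least 1843 patients (20% additional) will allow compensation for incomplete datasets". Discontinuation of TRAVATAN is a separate secondary endpoint in Section 3.2, and the flow chart records it at weeks 8 and 24. Neither Section 3.1 nor Section 10 states the denominator of the primary proportion.

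**The concern.** In a study of adherence, coming off the drug is close to the outcome itself. A rule that ends observation at that moment removes patients before the only time point at which the primary endpoint is read.

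The protocol's own text suggests that the loss is not random. Section 1.1 links problems with topical medication to poor compliance and to switching, and it says that regular use is needed for disease control. A patient who uses the drops poorly may therefore develop uncontrolled IOP, meet an exclusion criterion and be withdrawn before week 24. Section 1.1 also reports that "less than 60% continue to refill eye drop prescriptions at 1 year". That is neither a 24-week figure nor a TRAVATAN figure, but it shows that the authors regard stopping as common.

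Enrolling more patients restores the number with a score. It does not restore the kind of patient who was lost. If the withdrawn are omitted, the headline figure describes patients retained to week 24, while the objective in Section 1.3 concerns adherence under standard clinical practice.

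**Working it through.** **Inputs.** Expected proportion 0.80, margin 0.02, 95% confidence, 1537 required and 1843 total (all Section 9). The share withdrawn, q, and the share of the withdrawn who are highly adherent, r, are not in the protocol. Both are assumptions and are varied below.

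**Step 1: the plan's own figures.** n = 1.96² × p(1 − p) / d² = 1.96² × 0.80 × 0.20 / 0.02². With the unrounded normal quantile this is 1536.58, so 1537 is reproduced. Adding 20% gives 1536.58 × 1.2 = 1843.9, and 1536 × 1.2 = 1843.2, so 1843 is reproduced within rounding. The sample-size arithmetic is not at issue. The allowance absorbs a loss of 1 − 1537/1843 = 16.6%.

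**Step 2: what the allowance protects.** With 1537 patients retained, the half-width is 1.96 × √(0.80 × 0.20 / 1537) = 2.0 points. That holds whoever the lost patients are, so it says nothing about bias.

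**Step 3: gap between retained and all-enrolled proportions.** All-enrolled proportion = (1 − q) × 0.80 + q × r. The gap is therefore 0.80 minus this, which is q × (0.80 − r). In percentage points:

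| q | r = 0 | r = 0.2 | r = 0.4 | r = 0.6 | r = 0.8 |
|---|---|---|---|---|---|
| 2.5% | 2.0 | 1.5 | 1.0 | 0.5 | 0 |
| 5% | 4.0 | 3.0 | 2.0 | 1.0 | 0 |
| 10% | 8.0 | 6.0 | 4.0 | 2.0 | 0 |
| 16.6% | 13.3 | 10.0 | 6.6 | 3.3 | 0 |
| 20% | 16.0 | 12.0 | 8.0 | 4.0 | 0 |

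The gap equals the 2-point margin when q = 0.02 / (0.80 − r), which is 2.5% at r = 0, 5% at r = 0.4 and 10% at r = 0.6. The column r = 0 also gives the result when discontinuers are defined as not highly adherent. The all-enrolled proportion is then 72% at q = 10%, 68% at 15% and 64% at 20%.

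**Step 4: the MPR.** Section 5.5 divides untreated days by days in the study and calls a value below 0.20 high adherence. Withdrawal stops both counts. As an illustration, take a patient with no missed days who is taken off TRAVATAN and withdrawn at week 8 (8 × 7 = 56 days). The MPR is 0/56 = 0, which is high adherence. If the patient were followed to week 24 (168 days) without the drug, it would be (168 − 56)/168 = 0.67. This reads the medication in the definition as TRAVATAN.

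**The case against.** A reader might infer more than the protocol supports, in four ways.

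- **That withdrawn patients are classed as incomplete data and the proportion is computed only in patients still on the drug.** No section says so. Section 9 does not define an incomplete dataset, and no denominator is fixed. A SAP could count known discontinuers as failures, because discontinuation and its reason are recorded.
- **That everyone who stops is removed.** The first bullet of Section 7 depends on the investigator's decision. A patient who skips or stops drops unprompted is not withdrawn by it and can answer the week-24 questionnaire.
- **That the result is overstated as a matter of fact.** This depends on the target. Adherence while the drug is prescribed is a legitimate quantity, and someone withdrawn for pregnancy or hypersensitivity may have been fully adherent. Setting r = 0 combines adherence with persistence, so part of the gap is a difference between two definitions.
- **That the gap is known to be large.** No discontinuation rate is given. The one-year refill figure concerns glaucoma drops generally, not investigator-ordered stopping over 24 weeks in patients already on TRAVATAN with controlled IOP.

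All four limits stand. They do not answer the remaining point. Section 7 is a data-collection rule, and a SAP can only reclassify or impute what was not collected. It cannot recover the week-24 status of patients withdrawn under the exclusion-criterion bullet, some of whom may still be using TRAVATAN, nor the truncated MPR follow-up. Reporting discontinuation as a separate secondary endpoint informs the reader but corrects neither proportion.

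**Conclusion.** The concern holds as a conditional one. What is certain is that Section 7 leaves patients withdrawn under its first and third bullets without a week-24 MMAS-4, shortens their MPR follow-up, and is not offset by the over-enrolment. What is probable is that this loss is related to adherence, so that omitting these patients would overstate adherence among all enrolled.

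The size is q × (0.80 − r). At 10% withdrawn it is 8 points if none of the withdrawn are highly adherent, 4 points if 40% are, and 0 if they are as adherent as those retained. The planned margin is 2 points. This rests on three assumptions: 80% among retained patients, withdrawn patients left out of the denominator, and a score of 0 meaning high adherence as Section 3.1 states. The item coding in Section 5.4 (a Yes answer scored 0, a No answer scored 1) needs checking against that last assumption. The point should be settled before enrolment, because the uncollected data cannot be recovered afterwards.

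**What to change.** 1. **Section 7:** separate stopping TRAVATAN from leaving the study. Unless consent is withdrawn, keep collecting treatment status, and the MMAS-4 where it applies, at weeks 8 and 24. This changes data collection only, not care.
2. **Sections 3.1 and 10:** report the proportion of all eligible enrolled patients who are on TRAVATAN and highly adherent at week 24, with known discontinuers not counted as highly adherent. Beside it, give the on-treatment proportion, clearly labelled, and discontinuation by recorded reason.
3. **Section 5.5:** state whether days after discontinuation enter the MPR.
4. **Sections 6 and 7:** Section 6 permits any addition to concomitant medication, while Section 7 withdraws a patient who comes to meet an exclusion such as more than one ocular therapy. These passages must be reconciled.

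**Cost.** There is some extra follow-up of patients who would otherwise have left, and the headline figure will be lower. Precision also falls slightly. With all 1843 in the denominator, the half-width 1.96 × √(p(1 − p)/1843) is 2.05 points at 72%, 2.13 at 68% and 2.19 at 64%. Holding exactly 2 points would need about 1937, 2090 and 2213 patients respectively. The excess is small, so restating the precision in Section 9 is better than enrolling more patients.

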8.1 Definition of an adverse event

An AE is any untoward medical occurrence in a patient administered a pharmaceutical product, regardless of whether it has a causal relationship with this treatment. In this study, any AE occurring after the study patient has signed the informed consent form should be recorded and reported as an AE. An AE can, therefore, be any unfavourable and unintended physical sign, symptom, or laboratory parameter that develops or worsens in severity during the course of the study, or significant worsening of the disease under study or of any concurrent disease, whether or not considered related to the study drug. A new condition or the worsening of a pre-existing condition will be considered an AE. Stable chronic conditions (such as arthritis) that are present before study entry and do not worsen during the study will not be considered AEs. Accordingly, an AE can include any of the following:

- Intercurrent illnesses
- Physical injuries
- Events possibly related to concomitant medication
- Significant worsening (change in nature, severity, or frequency) of the disease under study or other pre-existing conditions. (Note: A condition recorded as pre-existing that is intermittently symptomatic [e.g., headache] and which occurs during the study should be recorded as an AE.)
- Drug interactions
- Events occurring during diagnostic procedures or during any washout phase of the study
- Laboratory or diagnostic test abnormalities that result in the withdrawal of the patient from the study, are associated with clinical signs and symptoms or a serious adverse event (SAE), or require medical treatment or further diagnostic workup, or are considered by the physician to be clinically significant.

8.2 *Definition of an Adverse Drug Reaction*

An adverse drug reaction is defined as a response to a medicinal product which is noxious and unintended. Response in this context means that a causal relationship between a medicinal product and an adverse event is at least a reasonable possibility. Adverse reactions may arise from use of the product within or outside the terms of the marketing authorisation or from occupational exposure. Conditions of use outside the marketing authorisation include off-label use, overdose, misuse, abuse and medication errors.

8.3 *Definition of a Serious Adverse Event*

A SAE is an AE occurring at any dose that results in any of the following outcomes or actions:

- Death (other than disease progression in this study)
- A life threatening AE (i.e., the patient was at immediate risk of death from the event as it occurred); does not include an event that, had it occurred in a more severe form, might have caused death
- Inpatient hospitalization or prolongation of existing hospitalization means that hospital inpatient admission and/or prolongation of hospital stay were required for treatment of an AE, or that they occurred as a consequence of the event. Hospitalizations scheduled for an elective procedure or for treatment of a preexisting condition that has not worsened during participation in the study will not be considered SAEs.
- Persistent or significant disability or incapacity (refers to a substantial disruption of one's ability to conduct normal life functions)
- A congenital anomaly/birth defect
- An important medical event that may not result in death, be life threatening, or require hospitalization, but may jeopardize the patient and may require medical intervention to prevent one of the outcomes listed in this definition. Examples of such events are intensive treatment in an emergency room or at home for allergic bronchospasm; blood dyscrasias or

convulsions that do not result in hospitalization; or the development of drug dependency or drug abuse. Note: Any suspected transmission of an infectious agent via a medicinal product is considered an important medical event.

An AE that does not meet any of the criteria for seriousness listed above will be regarded as a non-serious AE.

8.4 Recording and Reporting Adverse Events

Serious and non-serious Adverse Events that occur during the study period which are recorded in the patient's medical records or source documentation must be transcribed onto the CRF, regardless of the severity of the event. The clinical course of each AE will be monitored at suitable intervals until resolved or stabilized or returned to baseline, or until the patient is referred to the care of a health care professional, or until a determination of a cause unrelated to the study drug or study procedure is made. The onset and end dates, duration (in case of AE duration of less than 24 hours), action taken regarding study drug, treatment administered, and outcome for each AE must be recorded on the source documentation and transcribed onto the eCRF. The relationship of each AE to study drug treatment and study procedures, and the severity and seriousness of each AE, as judged by the physician, must be recorded as well.

To satisfy regulatory requirements, all serious adverse events regardless of judged relationship to treatment with TRAVATAN®, that occur during the study period, must be reported to the sponsor by the physician. The event must be reported within 24 hours of when the physician learns about it or, if the event occurs on a weekend or national holiday, on the next working day. Contact details of the sponsor are provided below:

“sponsor”

Completing the Adverse Events/Adverse Drug Reaction Form and reporting the event must not be delayed, even if not all the information is available. The physician does not need

to actively monitor patients for adverse events once the study has ended. Serious adverse events occurring to a patient after the treatment of that patient has ended should be reported to the sponsor if the physician becomes aware of them.

8.5 *Relationship of an Adverse Event to the Study Drug*

The relationship of an AE to the study drug is characterized as follows:

No reasonable possibility (not related)

This category applies to adverse events which, after careful consideration, are clearly due to extraneous causes (disease, environment, etc) or to adverse events, which, after careful medical consideration at the time they are evaluated, are judged to be unrelated to the study drug. The relationship of an adverse event may be considered “no reasonable possibility” if it is clearly due to extraneous causes or if at least 2 of the following apply:

- It does not follow a reasonable temporal sequence from the administration of the test drug.

- It could readily have been produced by the patient’s clinical state, environmental or toxic factors, or other modes of therapy administered to the patient.

- It does not follow a known pattern of response to the test drug.

It does not reappear or worsen when the drug is re-administered.

Reasonable possibility (related)

This category applies to adverse events for which, after careful medical consideration at the time they are evaluated, a connection with the test drug administration cannot be ruled out with certainty nor felt with a high degree of certainty to be related to the study drug. The relationship of an adverse event may be considered “reasonable possibility” if at least 2 of the following apply:

- It follows a reasonable temporal sequence from administration of the drug.

- It cannot be reasonably explained by the known characteristics of the patient’s clinical state, environmental or toxic factors, or other modes of therapy administered to the patient.

- It disappears or decreases on cessation or reduction in dose. There are important exceptions when an adverse event does not disappear upon discontinuation of the drug, yet drug relatedness clearly exists.

It follows a known pattern of response to the test drug.

8.6 *Pregnancy*

All pregnancies that occur during the study, or within 14 days of completion of the study, are to be reported immediately to the individual identified in the clinical study personnel contact information section of this protocol, and the physician must provide the LSO with the pregnancy form. The process for reporting a pregnancy is the same as that for reporting an SAE. All patients who become pregnant will be monitored to the completion or termination of the pregnancy. If the pregnancy continues to term, the outcome (health of the infant up to 8 weeks of age), including spontaneous or voluntary termination, details of birth, and presence or absence of any birth defect, congenital abnormalities, or maternal and newborn complications, will be reported to the sponsor. Any complication of pregnancy will be reported as an AE or SAE, as appropriate. For pregnancies of partners of men participating in the study, the Sponsor's Pharmacovigilance (PhV) Department will determine the procedure to appropriately follow up after notification as described above. All partners who become pregnant and provide appropriate consent to Sponsor's PhV will be monitored to the completion or termination of the pregnancy.

If the pregnancy does not continue to term, 1 of the following actions will be taken:

- For a spontaneous abortion, report an SAE.
- For an elective abortion due to developmental anomalies, report as an SAE.

- For an elective abortion **not** due to developmental anomalies, report on the pregnancy form.

9. Sample size

In order to calculate a 95% confidence interval for the proportion of patients reporting high adherence to TRAVATAN® at 24 weeks, which is expected to be 80% with a margin error (Δ) (Okeke et al, 2009) no more than 2%, the required sample size is at least 1537 patients. A total sample size of at least 1843 patients (20% additional) will allow compensation for incomplete datasets.

10. Statistical methods

Demographic and clinical/prognostic data of the patients at baseline will be described with numerical and graphical summary statistics. The statistical significance of the proportion of patients reporting high adherence to TRAVATAN® will be assessed using a binomial test and the respective 95% confidence interval (CI). For the secondary endpoints, categorical data will be analyzed using a binomial test with the respective 95% CI, and continuous data will be analyzed using the paired t-test or the Wilcoxon signed rank test, depending on the nature of the data. The association between categorical variables will be tested using a chi-squared test and/or logistic regression. A result will be considered significant when $P \leq 0.05$. The statistical analysis will be performed using SPSS v.21.

11. Insurance coverage

Since this is a non-interventional clinical study, an insurance coverage is not applicable.

12. Regulatory Authority approval

The protocol will be submitted for approval to the Scientific Committee of each participating clinical site. Approval by the Greek Regulatory Agency (Hellenic Organization for Medicines, EOF) is not required due to the nature of the study (phase IV).

13. Data collection – Quality control

Data will be entered at the study sites into a central database using an electronic CRF (eCRF) with a delegated CRO as an administrator.

The investigator should keep accurate files to record study conduction. Study documents will be kept by the investigator on site as confidential documents. All applicable data will be transferred to the patient's Case Report Form (CRF). The Case Report Form is essential for the study conduction and should be completed for all patients entering the study by the investigator. The Sponsor has the rights of the completed original CRFs and therefore data should not be released in any format without the prior written approval of the Sponsor. Monitoring visits by authorised personnel may take place at the site to ensure conduction of the study in accordance to the protocol and ICH GCP Guidelines. The study monitor will be given access by the investigator or sub-investigator to the patient files and any relevant documents to ensure source data verification and will be assisted in resolving any issues arisen during the monitoring visits.

The investigational site may also get quality control audits by the sponsor company or the Regulatory Authorities. The investigator will ensure access of any study related documents to the authorised personnel of the sponsor company or the Regulatory Authorities during the quality control audits. For the smooth conduction of the study, it is important that investigational staff will be available during the monitoring visits or the quality control audits.

14. Protocol Amendments and violations

No changes from the final approved (signed) protocol will be initiated without the prior written approval or favourable opinion of a written amendment by the scientific committees as applicable to local regulations.

Any significant deviation from the protocol will be considered a protocol violation. Protocol violations include non-adherence on the part of the patient, the physician, or the sponsor to protocol-specific inclusion/exclusion criteria. Protocol violations will be identified and recorded by investigational site personnel on the eCRF. If investigational site personnel learn that a patient who did not meet protocol eligibility criteria was entered into a study, they must immediately inform the sponsor of the protocol violation. If such patient has already completed the study or has withdrawn early, no action will be taken but the violation will be recorded.

15. Ethics

